10.2.1 Adverse Events of Interest

Adverse events of interest are defined in Appendix 4. Numbers and proportions of subjects with the following AEs of interest will be summarized by SOC and PT.

- Extrapyramidal AEs
- Neuroleptic malignant syndrome-related AEs
- Rhabdomyolysis
- Seizure-related AEs
- Orthostatic disorder-related AEs
- Suicide/suicide attempt-related AEs
- Oversedation-related AEs
- Hypersensitive symptom-related AEs
- Venous thrombosis
- Blood disorder-related AEs
- Glucose metabolism-related AEs
- Lipid metabolism-related AEs
- Body weight-related AEs
- QT interval prolongation-related AEs

- Manic switch-related AEs
- Prolactin increase-related AEs

10.2.2 Subgroup Analysis of Adverse Events

Numbers and proportions of subjects with TEAEs will be summarized by SOC and PT in each of the following subgroups:

- Requisite concomitant medications (duloxetine, escitalopram, fluvoxamine, milnacipran, paroxetine, sertraline, venlafaxine, mirtazapine)
- Sex (male, female)
- Impact of COVID-19 pandemic (subjects who completed/discontinued the trial before 07 Apr 2020, subjects who completed/discontinued the trial on or after 07 Apr 2020)

10.3 Clinical Laboratory Data

For each quantitative laboratory parameter, descriptive statistics of actual measurements and changes from baseline at each time point and the last assessment time point (Week 52 LOCF) will be calculated.

For each quantitative laboratory parameter, actual measurements will be classified as "lower than the lower limit of the reference range," "within the reference range," and "higher than the upper limit of the reference range" using the reference range specified by the central laboratory, and a shift table from baseline will be produced.

For each qualitative laboratory parameter, a shift table from baseline will be produced.

Numbers and proportions of subjects with laboratory test values not meeting the criteria for potentially clinically significant laboratory test values (Appendix 2) at baseline and meeting the criteria after treatment will be determined. A listing of these subjects will be provided.

Numbers and proportions of subjects with postdose values of alanine aminotransferase (ALT), aspartate aminotransferase (AST), and total bilirubin (TBL) meeting Hy's Law criteria (ALT or $AST \geq 3 \times$ the upper limit of normal [ULN] and $TBL \geq 2 \times$ ULN) will be determined. A listing of these subjects will be provided.

Numbers and proportions of subjects with a prolactin value not meeting the criteria of $> 1 \times$ ULN, $> 2 \times$ ULN, or $> 3 \times$ ULN at baseline and meeting the criteria after treatment will be determined by sex. A listing of these subjects will be provided.

Numbers and proportions of subjects with postdose values of fasting low-density lipoprotein (LDL) cholesterol, high-density lipoprotein (HDL) cholesterol, triglyceride, and blood glucose meeting the criteria for changes in glucose and lipid metabolism-

related parameters (Table 10.3-1) will be determined by baseline value. A listing of these subjects will be provided.

Table 10.3-1 Changes in Glucose and Lipid Metabolism-related Parameters		
LAB PARAMETER	BASELINE	ANYTIME POST BASELINE
LDL Cholesterol, Fasting (mg/dL)	Borderline 100-<160 Normal/Borderline <160 Normal <100 Any Value	High >=160 High >=160 Borderline/High >=100 Increased >=30
HDL Cholesterol, Fasting (mg/dL)	Normal >=40 Any Value	Low <40 Decreased >=20
Triglycerides, Fasting (mg/dL)	Normal <150 Borderline 150-<200 Normal/Borderline <200 Normal <150 Normal/Borderline/high <500 Any Value	High 200-<500 High 200-<500 High 200-<500 Borderline/High/Very High >=150 Very High >=500 Increased >=50
Glucose Fasting, Serum (mg/dL)	Normal <100 Impaired 100-<126 Normal/Impaired <126 Any Value	High >=126 High >=126 High >=126 Increased >=10

Numbers and proportions of subjects not meeting the metabolic syndrome criteria (Table 10.3-2) at baseline and meeting the criteria after treatment will be determined. A listing of these subjects will be provided.

Table 10.3-2 Metabolic Syndrome Criteria	
Description	Metabolic Syndrome Criteria (Health, Labour and Welfare Ministry of Japan)
Central obesity	Waist Circumference \geq 85 cm (Male), \geq 90 cm (Female)
Dyslipidemia	Triglycerides, Fasting \geq 150 mg/dL and/or HDL, Fasting <40 mg/dL
Supine blood pressure	Systolic \geq 130 mmHg and/or Diastolic \geq 85 mmHg
Glucose fasting, serum	\geq 110 mg/dL
Metabolic syndrome	Met central obesity criteria and 2 of 3 other criteria at a visit

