C-SSRS	•	• f	•	•	•	•	•	•	•	•	•	•	•	•	•	•	•	•	•	•	•	•	•	•
DIEPSS		• f	•	•	•	•	•	•	•	•	•	•	•	•	•	•	•	•	•	•	•	•	•	•
AIMS		• f	•				•				•									•	•			
BARS		• f	•				•				•									•	•			
Blood sampling for DNA storage						• i														• i				

Table 3.7-1		Schedule of Assessments																		
Test Period (Acceptable Window)	Items	Treatment Period															Post-treatment observation periodj 30 days after final dose (± 5 days)			
		At screening (new subjects)b	At baseline (rollover subjects)	At baseline (new subjects)	Week 1 (± 2 days)	Week 2 (± 2 days)	Week 4 (± 2 days)	Week 8 (± 7 days)	Week 12 (± 7 days)	Week 16 (± 7 days)	Week 20 (± 7 days)	Week 24 (± 7 days)	Week 28 (± 7 days)	Week 32 (± 7 days)	Week 36 (± 7 days)	Week 40 (± 7 days)		Week 44 (± 7 days)	Week 48 (± 7 days)	Week 52 (± 7 days)
Adverse events		←-----→																		
IMP and requisite concomitant medicationa				•	•	•	•	•	•	•	•	•	•	•	•	•	•	•	•	
Concomitant drugs/therapies		←-----→																		

a Treatment compliance regarding IMP and requisite concomitant medication will be recorded.

b Clinical laboratory test values and body weight values at screening will be used as baseline values.

c For this item, subjects will be asked to visit the trial site in a fasting state (a fast for at least 8 hours [including drinks containing sugar, such as juice]) at screening, baseline, and Week 52, and in a fasting state to the extent possible at other times, including at the discontinuation examination.

d Informed consent will be obtained after the observations, examinations, and assessments at Week 6 of the double-blind period (Phase B) of the double-blind trial (331-102-00058) and before the baseline assessments for this trial.

e Data taken at screening for the double-blind trial (331-102-00058) will be used as the subject demographic data for rollover subjects (date of birth, sex, childbearing potential, race, ethnicity, country where trial is performed, history of major depressive disorder, medical history, complications). Medical history and complications will be reinvestigated.

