#### **3.7.4.2 Clinical Laboratory Assessments**

##### (1) Time points

At screening (new subjects only, in the fasting state), baseline (rollover subjects only, in the fasting state), Weeks 4, 8, 16, 24, 32, and 40 (in the fasting state to the extent possible), and Week 52 (in the fasting state) or discontinuation (in the fasting state to the extent possible)

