##### (2) Method

Subjects will be asked to visit the trial site in a fasting state (a fast for at least 8 hours [including drinks containing sugar, such as juice]) at screening (new subjects only), baseline (rollover subjects only), and Week 52, and in a fasting state to the extent possible at other time points including examination at discontinuation.

Blood and urine samples will be collected from each subject at the time of clinical laboratory tests as specified in the assessment schedules shown in Table 3.7-1, and the date and time of blood sampling and the date of urine sampling as well as the fasting or fed state during blood sampling will be recorded in the source documents and the CRF. In this trial, the central laboratory selected by the sponsor will be used. Clinical laboratory test values determined at the central laboratory will be used for eligibility assessment. For appropriate procedures for the collection, handling, and shipment of samples, separately documented procedures will be prepared and provided prior to the start of the trial. The central laboratory will report the results of tests to the investigator or subinvestigator. The investigator or subinvestigator will confirm the results of tests and date and sign the

clinical laboratory test report to make it an official document. The results of laboratory tests, which will be reported directly from the central laboratory to the sponsor as an electronic file, do not need to be recorded in the source documents or the CRF.

Table 3.7.4.2-1 Clinical Laboratory Assessments	

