Hematology: Red Blood Cell count White blood cell count Differential count of white blood cells (neutrophils, eosinophils, basophils, monocytes, lymphocytes) Platelet count Hemoglobin Hematocrit  Urinalysis: pH Protein Glucose Occult blood Urobilinogen Specific gravity Ketone body	Serum Chemistry: AST (Glutamic oxaloacetic transaminase [GOT]) ALT (Glutamic pyruvic transaminase [GPT]) Alkaline Phosphatase (ALP) Lactic Dehydrogenase (LDH) Gamma-glutamyl transpeptidase ( $\gamma$ -GTP) Total protein Albumin Total bilirubin Cholesterol (total cholesterol, low-density lipoprotein [LDL] cholesterol, and high-density lipoprotein [HDL] cholesterol) Triglycerides Blood urea nitrogen (BUN) Creatinine Uric acid Creatine kinase (CK) (CPK) Serum electrolytes (Na, K, Cl, Ca, Mg, P, bicarbonate) Blood glucose HbA1c (NGSP value) Prothrombin time (PT) Activated partial thromboplastin time (APTT) PT (international normalized ratio [INR])  Endocrinology: Serum prolactin Insulin FT4 TSH

To be performed in subjects in a fasting state (a fast for at least 8 hours [including drinks containing sugar, such as juice]) at screening (new subjects only), baseline (rollover subjects only), and Week 52, and in a fasting state to the extent possible at other time points including examination at discontinuation

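### SAP 10.3 sets no fasting condition for the mean-change, shift and Week 52 LOCF summaries of glucose, lipids and insulin, so these may compare fed with fasting samples

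*SAP*

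**What the plan says.** SAP 10.3 opens with one rule for all quantitative tests: "For each quantitative laboratory parameter, descriptive statistics of actual measurements and changes from baseline at each time point and the last assessment time point", the last being Week 52 LOCF. Values are also classed as low, within range or high "using the reference range specified by the central laboratory, and a shift table from baseline will be produced". Neither sentence mentions fasting, and Protocol 7.7.2 adds no such condition.

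The rules that choose the values are equally silent. SAP 3.4 takes the last value in a visit window. SAP 5.3 carries the last post-dose value to Week 52. SAP 10 takes the last pre-dose value as baseline.

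The same section does use fasting elsewhere. It counts "subjects with postdose values of fasting low-density lipoprotein (LDL) cholesterol, high-density lipoprotein (HDL) cholesterol, triglyceride, and blood glucose meeting the criteria" of Table 10.3-1, where one row label begins "Glucose Fasting, Serum (mg/dL". The glucose and lipid components of Table 10.3-2 are fasting values. Appendix 2 labels its lipid criteria as fasting and gives glucose separate fasting and non-fasting limits.

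On sampling, footnote c of Protocol Table 3.7-1 asks subjects to attend fasting "at screening, baseline, and Week 52, and in a fasting state to the extent possible at other times, including at the discontinuation examination". Protocol 3.7.4.2 lists the softer visits as "Weeks 4, 8, 16, 24, 32, and 40 (in the fasting state to the extent possible"), treats discontinuation the same way, and states that "the fasting or fed state during blood sampling will be recorded in the source documents and the CRF". The endocrinology panel in Table 3.7.4.2-1 reads "Serum prolactin Insulin FT4 TSH", so insulin is measured.

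For rollover subjects, footnote f lets Phase B Week 6 results from the 7 days before baseline serve as baseline.

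**The concern.** The trial has no control group (Protocol 3.6), so change from baseline is the only comparison for laboratory means and shifts. If fasting state differs between baseline and a later visit, no other arm shares that difference and it cannot be subtracted out. A fasting baseline followed by a fed sample could look like metabolic drift. The reverse could hide one.

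The SAP itself treats fasting state as material: Appendix 2 flags glucose at 100 mg/dL fasting but 200 mg/dL non-fasting. Protocol 1.3 names dyslipidemia among the important potential risks, so readers will look at these tables. The Week 52 LOCF row is the most exposed. A value carried from an early leaver comes from a visit where fasting was not firmly required.

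**Working it through.** The plan states no figure to reproduce, so the check is a reading of the rules plus simple counts.

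**1. Visits by strength of the fasting request (Protocol 3.7.4.2).** Scheduled post-baseline laboratory visits are Weeks 4, 8, 16, 24, 32, 40 and 52, which makes 7. The request is firm at Week 52 only and softer at the other 6: 6/7 = 86%. Discontinuation is also softer.

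**2. Baseline.** For new subjects the screening sample is the baseline (Table 3.7-1, footnote b), and it is requested fasting. For rollover subjects the baseline sample is requested fasting, but a Phase B Week 6 sample may replace it. Rollover exclusion 16(b) gives a fasting limit of 126 mg/dL and a non-fasting limit of 200 mg/dL for that same Week 6 visit. Non-fasting samples were therefore foreseen there.

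**3. Following a value through the rules.**
- At Weeks 4 to 40, SAP 3.4 picks the last value in the window whatever its fasting state.
- If there is no Week 52 value, SAP 5.3 picks the last post-dose value. It comes from Weeks 4 to 40, from discontinuation or from an unscheduled test, again whatever its fasting state.
- Observed Week 52 values are largely safe. The exception is a discontinuation sample on Days 351 to 385, which SAP 3.4 would map to Week 52.

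**4. Where a fasting condition does exist in the SAP.**

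| Parameter | Table 10.3-1 | Table 10.3-2 | Appendix 2 |
|---|---|---|---|
| Glucose | yes | yes | yes |
| Triglycerides | yes | yes | yes |
| HDL cholesterol | yes | yes | yes |
| LDL cholesterol | yes | no | yes |
| Total cholesterol | no | no | yes |
| Insulin | no | no | no |
| Count of 6 | 4 | 3 | 5 |

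None of these three places governs the mean-change, shift or LOCF summaries. Insulin has no fasting-labelled analysis anywhere.

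**5. Size.** Let p be the non-fasting share among subjects in a change summary, at baseline and at the later visit. Let D be the mean fed-minus-fasting difference, assumed equal at both times. The distortion of the mean change is (p_post − p_base) × D. The documents give neither p nor D. Because p_base may be above zero for rollovers, even the sign is open.

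**The case against.** The strongest reply is that fasting results may already be separate parameters. Table 10.3-1 lists them in its parameter column, and Appendix 2 splits glucose into fasting and non-fasting. On that reading, a rule for each parameter already keeps them apart. This stands as a real possibility. Against it, the protocol panel lists blood glucose once. The serum chemistry titles in Appendix 5 (CT-10.1.1 and CT-10.2.1) carry no fasting qualifier, although prolactin is explicitly split by sex. Insulin has no fasting label under either reading.

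A second reply is that the main metabolic questions are already answered on fasting data, through categorical changes, metabolic syndrome and the Appendix 2 criteria. HbA1c is also measured. This stands in full and limits the point to the course of means, the shifts and LOCF, in a descriptive trial.

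A third concerns the 86%. A reader might infer that most later samples were fed. The documents do not support that: fasting is requested at every laboratory visit, and the figure counts visits with softer wording.

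A fourth concerns the remedy. A reader might infer that non-fasting samples should simply be removed. That would drop every rollover whose Week 6 baseline is not recorded as fasting, and would replace an early leaver's last value with an older one, contrary to Protocol 7.3 and SAP 5.3. The objection stands, and the fix avoids both effects.

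Finally, the documents request fasting for the whole panel and do not single out insulin. Including it with glucose and lipids is a judgement.

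**Conclusion.** The point holds in a limited form. Read as written, three summaries in SAP 10.3 may compare fed with fasting values for six parameters. The documents do not establish that they will, and they allow no estimate of how much or in which direction.

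The point assumes that the last-value rules apply to these parameters without an unstated fasting split, and that some samples at the softer visits or at rollover baseline are non-fasting. If glucose and lipids are already held as fasting parameters, what remains is to say so and to cover insulin.

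A reader might go further and infer that the glucose and lipid safety evidence is compromised. The documents do not support that, because the fasting categorical analyses and HbA1c are untouched and observed Week 52 values are largely so. This is a cheap improvement.

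**What to change.** Add to SAP 10.3:

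> For glucose, triglycerides, total, LDL and HDL cholesterol, and insulin, the mean-change, shift and Week 52 LOCF summaries are presented by recorded fasting status. The fasting summary uses pairs in which both the baseline and the post-baseline sample are recorded as fasting. The all-samples summary, with LOCF as defined in Section 5.3, is kept alongside, and the number of subjects without a fasting pair is shown.

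The cost is a few extra tables and a smaller n in the fasting summary. No subject leaves the all-samples summary, the protocol's LOCF rule is unchanged, and this trial's samples need no new data because their fasting state is already recorded.

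One dependency should be checked. Applying exclusion 16(b) implies that fasting state was known at Phase B Week 6, but these documents do not show whether it is available to this trial's analysis. Where it is not, those rollover subjects appear in the count without a fasting pair.

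Protocol 7 requires the SAP to be final before data lock, and the lock date is not given. If lock has passed, the fasting summary can be reported as a labelled supplement.

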### **1.3 Known and Potential Risks and Benefits**

Extrapyramidal symptoms, seizures, suicidality, and dyslipidemia have been assessed as important risks associated with the administration of brexpiprazole. The potential mechanism of antipsychotics causing seizures is a class effect thought to be due to a reduction of the seizure threshold in susceptible individuals. The occurrence of suicidal behavior is inherent in psychotic illnesses and mood disorders. In the schizophrenia and major depressive disorder populations, short-term and long-term administration of brexpiprazole was associated with moderate weight gain; however, weight gain did not contribute significantly to IMP discontinuation, and only a few subjects with marked weight gain demonstrated metabolic syndrome. Although not clinically significant, an increase in triglycerides was observed in some trials. Due to this observation and considerations on potential clinical consequences related to weight gain, dyslipidemia is considered to be an important potential risk.

With lower intrinsic activity at the D2 receptors and more potent effects on the serotonergic system, which is suggested to be involved in the improvement of depressive symptoms, extrapyramidal symptoms, and cognitive function, compared with aripiprazole, evidence suggests that brexpiprazole can reduce the incidence of AEs such as akathisia and other extrapyramidal symptoms, nausea, vomiting, excitement, and irritability, and also improve symptoms of depression. In clinical trials conducted overseas, the incidence of AEs, such as akathisia, which are considered risk factors for low adherence to treatment, was confirmed to be low in patients treated with brexpiprazole. Therefore, brexpiprazole is likely to become a useful treatment option for patients with major depressive disorder who need to receive treatment over a long period of time.

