43	
Patients meeting any of the following criteria
 
 
• Patients with type 1 diabetes mellitus or patients with type 2 diabetes mellitus being treated with insulin
 
• Patients with type 2 diabetes mellitus who have not been maintained on a stable regimen of anti-diabetic medication(s) or undergone diet/exercise therapy for at least 28 days prior to screening
 
• Patients meeting either of the following criteria for poor blood glucose control at screening (assessed based on results from the central laboratory) 
 
a) HbA1c of <math>\geq 8.0\%</math> according to the global standard value [NGSP value]
 
b) Fasting blood glucose level of <math>\geq 126</math> mg/dL or non-fasting blood glucose level of <math>\geq 200</math> mg/dL
 
 
 

44	Patients with substance abuse or substance dependence, including alcohol and benzodiazepines, based on DSM-5 diagnostic criteria within 180 days prior to informed consent; caffeine and nicotine are not included
45	Patients with a complication of hypothyroidism or hyperthyroidism at informed consent (excluding those in a stable condition due to medications for the previous 90 days or longer since acquisition of informed consent), or abnormal TSH and FT4 levels at screening (assessed based on results from the central laboratory)
46	
Patients meeting any of the following criteria or showing symptoms at screening or baseline
 
 
a) Poorly controlled hypertension (diastolic blood pressure of <math>> 95</math> mmHg)
 
b) Hypotension with symptoms
 
c) Orthostatic hypotension in which blood pressure after 3 minutes of standing is <math>\geq 30</math> mmHg lower for systolic blood pressure or <math>\geq 20</math> mmHg lower for diastolic blood pressure, compared with pressures in the supine position before standing
 

47	Patients with a complication of ischemic heart disease, myocardial infarction, or congestive heart failure (irrespective of well or poorly controlled), or patients with a history of angioplasty, stent placement, or coronary artery bypass
48	Patients with a history of neuroleptic malignant syndrome or serotonin syndrome
49	Patients with a history or complication of epilepsy or epileptic seizures, excluding pediatric febrile seizures, post-traumatic seizures, alcohol withdrawal seizures, and other seizures

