- Pregnancies are also defined as IREs. Although normal pregnancy is not an AE, it will mandate IMP discontinuation and must be reported on an IRE form to the sponsor. Pregnancy will only be recorded in the source documents and the AE Section of the CRF if there is an abnormality or complication. This applies both to pregnancies of subjects and pregnancies of subjects' partners.

Clinical Laboratory Assessment Value Changes: It is the investigator's or subinvestigator's responsibility to review the results of all laboratory tests as they become available. This review will be documented by the investigator's or subinvestigator's dated signature on the laboratory report. For each abnormal laboratory test result, the investigator or subinvestigator needs to verify whether this is an abnormal (ie, clinically relevant) change from baseline for that individual subject. This determination, however, does not necessarily need to be made the first time an abnormal value is observed. The investigator or subinvestigator may repeat the laboratory test or request additional tests to verify the results of the original laboratory tests. If this laboratory value is considered medically relevant by the investigator or subinvestigator (subject is symptomatic, requiring corrective treatment or further evaluation), or if the laboratory value leads to discontinuation or meets the criteria for an SAE, this is considered an AE.

Severity: Adverse events will be graded on a 3-point scale and reported. The intensity of an AE is defined as follows:

**1 = Mild:** Discomfort noticed, but no disruption to daily activity.

**2 = Moderate:** Discomfort sufficient to reduce or affect normal daily activity.

**3 = Severe:** Inability to work or perform normal daily activity.

IMP Causality: Assessment of causal relationship between an AE and the IMP:

**Related:** There is a reasonable possibility of a temporal and causal relationship between the IMP and the AE.

**Not related:** There is no temporal or reasonable relationship between the IMP and the AE.

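### Treatment-emergent metabolic syndrome is judged on measured values alone while most metabolic and blood-pressure drugs are permitted, so the emergent count can be too high or too low

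*SAP*

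**What the plan says.** SAP 10.3 plans this output: "Numbers and proportions of subjects not meeting the metabolic syndrome criteria (Table 10.3-2) at baseline and meeting the criteria after treatment will be determined". The composite in Table 10.3-2 is "Met central obesity criteria and 2 of 3 other criteria at a visit". Central obesity is a waist of at least 85 cm (men) or 90 cm (women). The other three components are:

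- fasting triglycerides of at least 150 mg/dL and/or HDL below 40 mg/dL
- supine pressure of at least 130 mmHg systolic and/or 85 mmHg diastolic
- fasting serum glucose of at least 110 mg/dL

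No component refers to drug treatment, and no rule covers a drug started or changed after baseline. The denominator is not stated. The results go to tables CT-10.8.1 (incidence) and CT-10.8.2 (listing).

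On drug use, the protocol says the following:

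- Sections 3.4.3 (nos. 16 and 43): insulin-treated diabetes and type 2 diabetes without a stable regimen (or diet/exercise therapy) for 28 days are excluded. Stable non-insulin treatment may enter.
- Sections 3.4.3 (nos. 19 and 46; 15 and 42): hypertension is excluded only when poorly controlled (diastolic above 95 mmHg). Mild or well-controlled metabolic and cardiovascular disorders may enter.
- Sections 4.1 and 4.3: no lipid-lowering, antidiabetic or general antihypertensive class is prohibited or restricted. Beta-blockers are allowed only for cardiovascular disease, at the dose and regimen in use at consent.
- Section 4.4: diltiazem and verapamil are to be avoided.
- Section 3.7.4.2: after baseline, fasting is firmly required only at Week 52. At Weeks 4, 8, 16, 24, 32 and 40, and at discontinuation, it is asked for where feasible.

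**The concern.** The output depends on two classifications, one at baseline and one afterwards. A drug that lowers a measured value can change either. If it hides a component at baseline, a subject who already has the syndrome on a treatment-inclusive view is treated as free of it and can emerge later on a small rise. If a drug is started during the trial, a component that appeared may be gone before a second one is present, or before the next fasting sample.

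Treatment in response to findings is foreseeable. Protocol 5.1 describes medically relevant laboratory changes as those where the "subject is symptomatic, requiring corrective treatment or further evaluation" condition applies. The output also matters: Protocol 1.3 states that "dyslipidemia is considered to be an important potential risk", and supports its account of weight gain by saying that few subjects with marked gain showed metabolic syndrome. CT-10.8.1 is this trial's dedicated table on that question.

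**Working it through.** The plan gives no figure that depends on this definition, so there is nothing to reproduce. The check applies the Table 10.3-2 rule to constructed subjects, first on measured values alone and then with a component also counted as met while a drug for it is in use. All three subjects are centrally obese throughout, with HDL 50 mg/dL.

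**Subject A, false emergent case.** At baseline triglycerides are 160, blood pressure is 124/78 on an antihypertensive, and glucose is 100.
- Measured only: lipid yes, pressure no, glucose no. That is 1 of 3, so not met.
- Treatment-inclusive: lipid yes, pressure yes, glucose no. That is 2 of 3, so met, and A cannot become a new case.
- Systolic pressure later reads 131. Measured only: 2 of 3, so A is an emergent case after a 7 mmHg change (131 − 124).

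**Subject B, case never counted.** At baseline triglycerides are 120, pressure is 120/75 and glucose is 98. Pressure stays at 120/75.
- Week 8: triglycerides 210, glucose 98. That is 1 of 3. A lipid-lowering drug is started.
- Week 16: triglycerides 130, glucose 114. Measured only: 1 of 3. Treatment-inclusive: 2 of 3.
- Measured only, B never qualifies. Treatment-inclusive, B is counted at Week 16.

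**Subject C, a limit on the concern.** Baseline is as for B. At Week 8 triglycerides are 210 and glucose is 114, then both are normalised by drugs (130 and 100).
- If the Week 8 sample was fasting, C has 2 of 3 at that visit and is counted. Later treatment does not remove the case.
- If the Week 8 sample was not fasting, the lipid and glucose limits cannot be applied, and the Week 52 fasting values are normal. C is not counted.

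**Illustration of baseline misclassification.** The documents give neither input, so both are assumed. Let q be the true prevalence of each of the three components among centrally obese subjects, and let t be the fraction of affected subjects whose drug keeps the value below its limit. Treat the components as independent.

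P(at least 2 of 3) = 3q²(1 − q) + q³

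For the measured-only rule, replace q by q(1 − t). The share of baseline cases missed is 1 − P(measured)/P(true). For q = 0.3 and t = 0.2, P(true) = 3(0.09)(0.7) + 0.027 = 0.216. With q(1 − t) = 0.24, P(measured) = 0.145, so the share missed is 32.8%.

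| t | q = 0.3 | q = 0.4 | q = 0.5 |
|---|---|---|---|
| 0.05 | 8.6% | 8.1% | 7.5% |
| 0.10 | 17.0% | 16.1% | 14.9% |
| 0.20 | 32.8% | 31.3% | 29.6% |
| 0.40 | 60.4% | 58.8% | 56.8% |

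These are shares of centrally obese baseline cases missed. They are not errors in the emergent count, which also depends on how many of those subjects later cross a limit and on how many cases like B and C occur.

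**Weight of one subject.** 1/30 = 3.3 percentage points for 30 new elderly subjects; 1/100 = 1 point per 100 subjects. If the denominator is restricted to subjects not meeting the criteria at baseline, it is no larger than this and each subject weighs at least as much.

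**The case against.** The strongest reply is that this is one descriptive composite in an uncontrolled trial with no primary or secondary outcome variables (SAP section 6), and that the same risk is seen elsewhere. Under Protocol 5.1 a laboratory value needing corrective treatment is itself an adverse event. SAP Appendix 4 lists raised triglycerides, dyslipidaemia and metabolic syndrome as terms of interest, tabulated in CT-8.9.11 and CT-8.9.12. Mean changes, shift tables and CT-10.3.1 cover the individual parameters, and a triglyceride rise on a fasting sample is captured by Table 10.3-1, which looks at any time after baseline. Concomitant drugs are tabulated by class and preferred term, before, during and after treatment (SAP 7.5). All of this stands. It means that a treated subject may be missing from CT-10.8.1, not from the whole safety record. It does not correct baseline status in that table, it relies partly on investigator reporting, and no planned table links drug use to metabolic status or identifies new starts.

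It can also be said that the table applies named national ministry criteria. Whether that source has a treatment clause cannot be settled from the documents. The point does not depend on it, because the proposed addition leaves the measured-only result in place.

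A reader might infer more than the documents support:

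- That every case with exactly two of the three components is lost once one is treated. It is not: meeting the rule at one post-baseline visit is enough, as subject C shows.
- That a medicated diabetic whose fasting glucose moves from 105 to 112 mg/dL is a false new case. That requires central obesity and another component as well, and the rise is a real measured change.
- That the risk is understated. A inflates the count; B and C deflate it.
- That these drugs are expressly allowed during the trial. Lipid-lowering drugs and most antihypertensives are permitted only because no list names them.

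**Conclusion.** The point holds as a limited weakness in one safety output. Applied exactly as written, Table 10.3-2 can class a treated subject as free of metabolic syndrome at baseline, and can miss a subject treated before the components coincide at a visit with a fasting sample. Only some treated subjects are affected: those with central obesity in whom the drug-controlled component decides whether two of three are met.

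The net direction is unknown and the size cannot be derived. The illustrative shares (about 8 to 33% of centrally obese baseline cases missed when 5 to 20% of affected subjects are drug-controlled) rest wholly on assumed prevalence, assumed control and independence. Sample size, power and error rates are not touched.

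**What to change.** Keep the measured-only result in CT-10.8.1 and make three additions to the SAP:

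1. **Treatment-inclusive version in CT-10.8.1.** A component is met at a visit if the measured limit is met or a drug whose recorded purpose is that component (lipid, blood pressure or glucose) is in use. Apply this at baseline and afterwards.
2. **Denominator.** State it as subjects not meeting the criteria at baseline, separately for each version.
3. **New-treatment row in CT-10.6.1, CT-10.7.1 and CT-10.8.1.** Show the number of subjects who newly started or increased such a drug after Day 1.

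If the two versions agree, the result does not depend on treatment; if they differ, the reader sees by how much.

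The cost is small. Protocol 3.7.5 already collects drug, purpose, dose and start and end dates, and SAP 7.5 already codes the drugs. What remains is mapping drug classes and purposes to components. The downside is that work and a slightly smaller at-risk group in the treatment-inclusive version. No additional data collection is needed.
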